#### **5.1.7 Subgroup analysis**

For the integrated analysis, the overall summary of Adverse events, the incidence of all AEs and SAEs by primary system organ class and preferred term tables will be repeated by age of onset ( $\leq 6$  months,  $>6$  months).

## **5.2 Clinical laboratory data**

The following clinical laboratory parameters are to be assessed:

- Blood chemistry: total protein, albumin, creatinine, cystatin C, creatine phosphokinase, blood urea nitrogen, total serum bilirubin (direct and indirect), alkaline phosphatase, alanine aminotransferase, aspartate aminotransferase, glucose, calcium, phosphorus, chloride, sodium, potassium, bicarbonate, creatine kinase (MB [isoenzyme expressed in the myocardium], BB [isoenzyme predominantly expressed in the brain], and MM [isoenzyme expressed in skeletal muscle]), gamma-glutamyl transferase
- Hematology: red blood cells, hemoglobin, hematocrit, platelets, white blood cells, white blood cell differential
- Urinalysis: specific gravity, pH, protein, glucose, ketones, bilirubin, red blood cells, white blood cells, epithelial cells, bacteria, casts, crystals
- Total urine protein
- Coagulation parameters (aPTT, PTT, and INR) will be collected.

As described below, laboratory data will be examined using an analysis of “shifts” and changed from baseline by windowed visits. However, further analyses may be undertaken to more fully characterize potential laboratory safety signals, such as assessment of timing, recovery, reversibility, association with AEs, etc.

Each subject's laboratory values will be classified according to whether the test result is "low" (i.e., below the lower limit of normal [LLN]), "normal" (within the normal range), or "high" (i.e., above the upper limit of normal [ULN]). If a subject is missing a baseline value but had a post-baseline value, then the baseline assessment is labeled as "unknown". Likewise, if a subject had a baseline value but had no post-baseline values, then the minimum and maximum are labeled as "unknown". Post-baseline laboratory results are defined as any assessment taken after the first dose, including data collected from local laboratories. The shifts (relative to the normal range) from baseline to the minimum and maximum post-baseline values will be presented. Should a treatment affect a laboratory parameter, that parameter could be affected at different times for different subjects. Therefore, these analyses present the most extreme values for each subject. For many laboratory parameters, the effect could be in either direction, (i.e., an increase or a decrease), so both the maximum and minimum values have been analyzed. Based on values from the laboratory parameters, the shifts (relative to the normal range) from baseline to low and high will be calculated. If a subject's value shifts, it can change from normal to either low or high, from low to normal or high, from high to normal or low, or from unknown to low, normal, or high. For each parameter, the incidence of shift to low will be summarized using the minimum post-baseline values. Shift to low includes subjects with a normal, high, or unknown baseline value and at least one post-baseline value of the given test. Similarly, the incidence of shift to high will be summarized using the maximum post-baseline values. Shift to high includes subjects with a low, normal, or unknown baseline value and at least one post-baseline value.

For many parameters processed centrally, the laboratory has additional ranges, e.g., a notification to the site by telefacsimile that the subject's result is far enough outside the normal range to warrant notification, and/or a panic alert involving a telephone call made to the investigational site to notify them that the subject's result is outside of the normal range with potentially critical implications for the subject (see the table below). With the exception of liver function tests, should such ranges be available for a parameter, these additional categories will be presented in listings. For shift tables of laboratory parameters, those additional categories will be combined with the conventional categories. Specifically:

- LT (Low – telefacsimile) and LP (Low panic) will be classified as L (Lower limit of normal)
- HT (High – telefacsimile) and HP (High panic) will be classified as H (Upper limit of normal)

For liver function tests, the additional categories will be defined to present the baseline and post-baseline values as within the upper limit of normal, >1 to < 3 x ULN, >3 to 5 x ULN, > 5 to 10 x ULN, >10 to 20x ULN. For shift tables of laboratory parameters, additional categories will be combined with the conventional categories. Specifically, >20x ULN for ALT/AST; >1 to 1.5 x ULN, >1.5 to 2 x ULN, and >2 x ULN for total bilirubin; and >1 to 1.5 x ULN and >1.5 x ULN for alkaline phosphatase. In addition, shift from baseline in ALT and AST will be summarized by elevation in bilirubin (maximum post-baseline bilirubin >1.5 x ULN and >2 x ULN).

The minimum, median and maximum versus time profiles (windowed visits) for some laboratory parameters of interest will be presented graphically.

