- ⁹ At the evaluations scheduled for injection of study treatment or sham procedure, subjects will be assessed for the following growth parameters: body length, head circumference, chest circumference, and arm circumference.
- ¹⁰ Neurological examinations include assessment of mental status, level of consciousness, sensory function, motor function, cranial nerve function, and reflexes.
- ¹¹ Neurological examinations will occur between 4 to 6 hours after the injection of study treatment or sham procedure.
- ¹² Blood chemistry, hematology, and urinalysis panels.
- ¹³ Samples for safety laboratory tests will be collected before the injection of study treatment or sham procedure on Days 64 and 183 only.
- ¹⁴ End of Part 1 safety laboratory tests may be performed locally in addition to centrally to accommodate the Part 2 Day 1 dosing.
- ¹⁵ Refer to [Table 5](#) for CSF PK sample schedule. The CSF samples will be analyzed for Nusinersen concentrations. The remaining CSF sample will be stored for optional future biomarker analyses.
- ¹⁶ Blood samples for PK assessment will be collected 4 hours (± 1 hour) after the injection of study treatment or sham procedure only on Day 1. Refer to [Table 5](#) for the plasma PK sample schedule.
- ¹⁷ Blood samples for PK assessment will be collected before the injection of study treatment or sham procedure on Days 64 and 183 only. Refer to [Table 5](#) for the plasma PK sample schedule.
- ¹⁸ Overnight stay (at least 24 hours) is required after the first injection of study treatment or sham procedure. Following all subsequent injections or sham procedures, a stay of at least 6 hours at the study site is required; overnight stays are optional on these days.
- ¹⁹ In addition to concomitant medications, ancillary procedures will be recorded.
- ²⁰ AEs and SAEs will be collected in the case report form from the time of signing of the informed consent form as described in [Section 15.3.1](#) and [Section 15.3.2](#).

CONFIDENTIAL

The information contained herein may not be used, disclosed, or published without the written consent of Biogen MA Inc.

4.2.2. Schedule of Events: Part 2

Table 3: Part 2 Schedule of Activities for Subjects Randomized to Receive Nusinersen in Part 1

Study Period	Part 2 Treatment/Follow-Up									
	Study Day	Day 1			Day 2 ¹	Days 120, 239, 358, 477, 596, 715 (± 7 days) ²			Days 121, 240, 359, 478, 597, 716 ¹	Part 2 Final Follow-Up (Day 835 [± 7 days]) ³ or Part 2 Early Termination ⁴

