³ The Part 2 Final Follow-up Evaluation will occur 4 months after the last injection of study treatment, which will either be on Day 716 or later, if Part 2 of the study continues beyond Year 2.

⁴ Subjects who terminate early will be encouraged to complete the safety evaluations scheduled for the Part 2 Early Termination Evaluation.

⁵ Inclusion/Exclusion Criteria, Informed Consent, and CSF PK must be performed on Part 2 Day 1.

⁶ Vital signs include resting systolic and diastolic blood pressure, pulse rate, respiratory rate, temperature, pulse oximetry, and transcutaneous carbon dioxide. Pulse oximetry and transcutaneous carbon dioxide will be measured predose at each evaluation.

⁷ If Part 2 Day 1 study treatment injection is delayed more than 24 hours after the End of Part 1 visit, the following procedures must be done on Part 2 Day 1 predose: vital signs, weight, growth parameters, physical examination, ventilator use, neurological examination, and CSF PK. If Part 2 Day 1 study treatment injection is delayed more than 24 hours after End of Part 1 due to an AE, SAE, or other safety concern, or if Part 2 Day 1 study treatment injection is delayed more than 30 days after End of Part 1 for any reason, the following procedures must be done on Part 2 Day 1 predose: vital signs, weight, growth parameters, physical examination, ventilator use, neurological examination, ECG, CSF PK, and safety laboratory tests. Immunogenicity testing must also be repeated predose if Part 2 Day 1 study treatment injection is delayed more than 30 days after End of Part 1 for any reason.

⁸ Vital signs (resting systolic and diastolic blood pressure, pulse rate, respiratory rate, temperature, and pulse oximetry) will be collected 1 hour (± 15 minutes) after the injection of study treatment.

⁹ At the evaluations scheduled for injection of study treatment, subjects will be assessed for the following growth parameters: body length, head circumference, chest circumference, and arm circumference. Growth parameters and weight are to be collected at the same time.

¹⁰ Neurological examinations include assessment of mental status, level of consciousness, sensory function, motor function, cranial nerve function, and reflexes. If sedation was used, please allow sufficient recovery time for the subject to be fully engaged in the examination because it is important that the data collected truly reflect the subject’s neurological performance.

CONFIDENTIAL

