The information contained herein may not be used, disclosed, or published without the written consent of Biogen MA Inc.

- ¹¹ Predose and postdose.
- ¹² ECG will be performed on Days 239, 477, and 715, and at the Part 2 Final Follow-up Evaluation. ECG must be performed before obtaining blood samples for safety laboratory tests.
- ¹³ Blood chemistry, hematology, urinalysis, urine total protein panels, and coagulation parameters. Urine total protein and coagulation parameters will be assessed by local laboratories.
- ¹⁴ Samples for safety laboratory tests will be collected before the injection of study treatment at each dosing visit.
- ¹⁵ Blood samples for immunogenicity testing will be collected before the injection of study treatment on Days 239, 477, and 715.
- ¹⁶ Refer to [Table 6](#) for CSF PK sample schedule. The CSF samples will be analyzed for Nusinersen concentrations. The remaining CSF sample will be stored for optional future biomarker analyses.
- ¹⁷ Blood samples for PK assessment will be collected 4 hours (± 1 hour) after the injection of study treatment only on Day 1. Refer to [Table 6](#) for the plasma PK sample schedule. Plasma PK samples will be collected predose on Days 239, 477, and 715.
- ¹⁸ The optional assessment of sibling SMA data collection will be performed only after obtaining consent.
- ¹⁹ In addition to concomitant medications, ancillary procedures will be recorded.
- ²⁰ AEs and SAEs will be collected in the case report form from the time of signing of the informed consent form as described in [Section 15.3.1](#) and [Section 15.3.2](#).

CONFIDENTIAL

The information contained herein may not be used, disclosed, or published without the written consent of Biogen MA Inc.

Table 4: Part 2 Schedule of Activities for Subjects Randomized to Receive Sham Procedure in Part 1

Study Period	Part 2 Treatment/Follow-Up															
	Day 1			Day 2 ¹	Day 15 (±1 day)			Day 16 ¹	Day 29 (±1 day)			Day 30 ¹	Days 64, 183, 302, 421, 540, 659, 778 (±7 days) ²			Days 65, 184, 303, 422, 541, 660, 779 ¹
Study Day	Predose ⁵	LP	Postdose		Predose	LP	Postdose		Predose	LP	Postdose		Predose	LP	Postdose	
Informed Consent	X ⁵															
Inclusion/Exclusion Criteria	X ⁵															
Vital Signs ⁶	X ⁷		X ⁸	X ⁹	X		X ⁸		X		X ⁸		X		X ⁸	X
Weight	X ⁷			X	X				X				X			X
Growth Parameters ¹⁰	X ⁷				X				X				X			X
Physical Examination	X ⁷				X				X				X			X
Ventilator Use	X ⁷			X	X			X	X			X	X			X

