6. STUDY OBJECTIVES AND ENDPOINTS

6.1. Primary Objectives and Endpoints

Part 1

The primary objective of Part 1 of this study is:

- To assess the safety and tolerability of Nusinersen in subjects with SMA who are not eligible to participate in the clinical studies ISIS 396443-CS3B or ISIS 396443-CS4.

CONFIDENTIAL

The information contained herein may not be used, disclosed, or published without the written consent of Biogen MA Inc.

The endpoints that relate to this objective are:

- Incidence of AEs and SAEs
- Change from baseline (see Section 16.1) in clinical laboratory parameters, electrocardiograms (ECGs), and vital signs
- Change from baseline (see Section 16.1) in neurological examination outcomes

Part 2

The primary objective of Part 2 of this study is:

- To assess the long-term safety and tolerability of Nusinersen in subjects with SMA who participated in Part 1 and completed their End of Part 1 Evaluation assessments.

The endpoints that relate to this objective are:

- Incidence of AEs and SAEs
- Change from baseline (see Section 16.1) in clinical laboratory parameters, ECGs, vital signs, and growth parameters
- Change from baseline (see Section 16.1) in neurological examination outcomes
- Coagulation parameters (activated partial thromboplastin time [aPTT], partial thromboplastin time [PTT], and international normalized ratio [INR]) and urine total protein

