14.2. Laboratory Safety Assessments

The following laboratory tests will be performed to evaluate the safety profile of ISIS 396443:

- Blood chemistry: total protein, albumin, creatinine, cystatin C, creatine phosphokinase, blood urea nitrogen, total bilirubin (direct and indirect), alkaline phosphatase, alanine aminotransferase, aspartate aminotransferase, glucose, calcium, phosphorus, chloride, sodium, potassium
- Hematology: red blood cells, hemoglobin, hematocrit, platelets, white blood cells, white blood cell differential
- Urinalysis: specific gravity, pH, protein, glucose, ketones, bilirubin, red blood cells, white blood cells, epithelial cells, bacteria, casts, crystals

CONFIDENTIAL

The information contained herein may not be used, disclosed, or published without the written consent of Biogen MA Inc.

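### Urine total protein, a Part 2 primary safety endpoint, largely lacks a scheduled baseline, and SAP 5.2 counts an unknown baseline followed by a high value as a shift to high

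*SAP*

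**What the plan says.** Protocol 6.1 lists among the Part 2 primary endpoints "Coagulation parameters (activated partial thromboplastin time [aPTT], partial thromboplastin time [PTT], and international normalized ratio [INR]) and urine total protein". SAP 1.1 (Primary Objectives and Endpoints) repeats this.

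The safety laboratory panels differ between the two parts. For Part 1, including the End of Part 1 visit, Protocol Table 2 footnote 12 gives "Blood chemistry, hematology, and urinalysis panels". For Part 2, Table 3 footnote 13 and Table 4 footnote 14 give "Blood chemistry, hematology, urinalysis, urine total protein panels, and coagulation parameters".

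On Part 2 Day 1 the safety laboratory cell carries footnote 7 in both Part 2 tables. That footnote makes these tests mandatory before dosing in two cases: when the injection is "delayed more than 24 hours after End of Part 1 due to an AE, SAE, or other safety concern", or when it is more than 30 days late for any reason. The unconditional Day 1 list (footnote 5) contains no laboratory test.

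SAP 5.2 states that "laboratory data will be examined using an analysis of" shifts and of change from baseline by windowed visit. A missing baseline is labelled unknown, a move from unknown to any classified level counts as a shift, and the shift-to-high summary uses each child's maximum post-baseline value. On who enters that summary: "Shift to high includes subjects with a low, normal, or unknown baseline value and at least one post-baseline value".

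**The concern.** A shift table is meant to separate abnormality that arose after dosing from abnormality that was already there. Counting unknown baselines as eligible to shift does little harm when a few values are missing by accident. Here the gap is produced by the schedule and covers a whole treatment group. A child whose urine protein was high before any nusinersen, and is high once afterwards, is then tabulated as having shifted to high.

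The other analysis promised in SAP 5.2, change from baseline, cannot be computed for these children. The sham Part 1 column of the integrated safety display has no scheduled urine total protein either, so that test has no concurrent background rate. What is at stake is the reading of a safety signal on an endpoint that was placed on the primary list.

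**Working it through.** The plan states no figure to reproduce, and the sample size is not power-based. The check is a trace of the schedule and the rule, followed by an illustration of size.

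**1. Is a value scheduled before the first Part 1 dose?** No. Table 2 footnote 12 omits urine total protein, and the superseded protocol versions 1 to 3 bound with the current one do not list it in any panel. Section 14.2 of version 4 and the synopsis name it without separating the parts, but section 14 refers timing to Tables 2 to 4.

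**2. Is a value required before the first Part 2 dose?** Only under the two footnote 7 delays. Table 3 footnote 14 and Table 4 footnote 15 ask for a pre-injection sample whenever a child is dosed. Read alone they could reach Day 1, but they are attached to the later-visit columns, while the Day 1 cell carries footnote 7.

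**3. Which baseline applies?**
- Integrated analysis, previous nusinersen (planned n = 14): SAP 2 counts them from the first Part 1 dose, and Protocol 16 assigns the Part 1 baseline. By step 1 it is unknown, however step 2 is read.
- Part 2 baseline, both groups (including the planned 7 previous-sham children in the integrated Total): by step 2 it is unknown for children without a qualifying delay, unless the later-visit footnotes are taken to cover Day 1.

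**4. What does the rule then give?** If all n baselines are unknown, a child counts as a shift to high exactly when the maximum post-baseline value exceeds the upper limit of normal. The incidence therefore equals the proportion ever high.

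**5. Size of the artefact.** Let p be the share of children already high before dosing who are high at least once afterwards. This is an assumption, since the documents give no rate. Expected wrongly counted = n × p; chance of at least one = 1 − (1 − p)^n.

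| Group (planned n) | p = 5% | p = 10% | p = 20% |
|---|---|---|---|
| Previous nusinersen (14) | 0.70; 51% | 1.40; 77% | 2.80; 96% |
| Previous sham (7) | 0.35; 30% | 0.70; 52% | 1.40; 79% |
| Total (21) | 1.05; 66% | 2.10; 89% | 4.20; 99% |

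The rows for 7 and 21 assume that no previous-sham child has a Day 1 value.

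**6. Example.** Two persistently high children among 14 give 2/14 = 14.3% under the SAP rule. With measured baselines both would leave the shift-to-high set, giving 0/12.

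**The case against.** The strongest defence is that this is a disclosed and conservative convention. It matches SAP 5.1, where an adverse event whose onset cannot be placed is assumed to follow the first dose, and SAP 5.2 never calls a laboratory shift treatment-emergent. A full shift table can display the unknown category. Protocol 16.2.2.5 already plans laboratory summaries by visit and over time, and SAP 5.2 leaves room for further characterization. The urine total protein endpoint is not worded as a change from baseline. The analysis is descriptive, in at most 21 children.

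Most of this stands and limits the point. Reporting the values over time is sound, and a reader of the full shift table could see the unknowns. Nor is background wholly absent, as a reader might infer: urinalysis protein, a different test, is scheduled at Screening, Days 64 and 183 and End of Part 1, including in sham children. The defence does not rescue the shift incidence summary, which merges unknown with low and normal baselines. A convention suited to sporadic gaps gives a misleading label when a whole group has no baseline by schedule.

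**Conclusion.** The point holds for urine total protein. For previous-nusinersen children in the integrated analysis the baseline is unknown by design. For the Part 2 baselines most will be unknown unless the later-visit footnotes are read to cover Day 1. The incidence of shift to high then measures the proportion ever high. The artefact is 0.7 to 2.8 of 14, or about 1.1 to 4.2 of 21, at an assumed 5% to 20% already high, using planned group sizes.

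Three stronger readings are tempting, and the documents do not support them.

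- **That every high value is a false shift.** A child who was normal before dosing and high later is a genuine shift even with a measured baseline. Only the share already high is artefact.
- **That bicarbonate, creatine kinase isoenzymes and gamma-glutamyl transferase share the defect.** The version 3 chemistry list closes with "aspartate aminotransferase, glucose, calcium, phosphorus, chloride, sodium, potassium" and lacks them. Version 4 section 14.2, however, places them under blood chemistry, which Table 2 schedules in Part 1. Only a late arrival of version 4 would remove their baseline. The SAP suggests this, since WHO milestones and ACEND came in only with version 4, but no date is given against each child's Part 2 start.
- **That the first urine total protein value falls on Day 15 (previous sham) or Day 120 (previous nusinersen).** Those are version 4 timings; version 3 had no such test in Part 2. A later rollout would delay the first value and would not alter the conclusion.

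Coagulation is less affected: it is tested at Part 1 Screening, and Protocol 16.2.2.6 requires it before dosing.

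**What to change.** In SAP 5.2:

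1. Remove unknown baselines from the numerator and denominator of both the shift-to-low and shift-to-high incidence.
2. Add a separate row for baseline unknown with a high (or low) post-baseline value, and state the number of children with a baseline for each analyte.
3. For urine total protein, report values over time and the proportion ever high instead of shifts, and list each child's results beside the End of Part 1 urinalysis protein result. Do the same (values over time and proportion ever high) for any analyte added in version 4 that the data show has no baseline.
4. Reconcile footnote 7 with Table 3 footnote 14 and Table 4 footnote 15, and state which Part 2 Day 1 values qualify as baseline.

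Adding the test to the End of Part 1 panel is not an option, because SAP 1 and 1.3 record that Part 1 has ended.

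The cost is SAP wording and one extra table row, with no new data. The downside is that the few children whose baselines are missing by accident leave the shift incidence and appear in their own row.

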### **5.3 ECG**

ECGs are assessed at a central reading laboratory, and the results provided back to sites to be entered into the eCRF. ECG qualitative results include an overall interpretation of 'normal', 'abnormal but not clinically significant' or 'abnormal and clinically significant'. Quantitative results will not be captured in the clinical database.

The number and percentage of subjects with shifts from normal to each of the categorical values denoting an abnormal scan (abnormal not AE, abnormal AE) will be summarized by treatment group. A listing of subjects with abnormal status in ECG will be presented.

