The information contained herein may not be used, disclosed, or published without the written consent of Biogen MA Inc.

Statistical Methods: Analysis Population

The intent-to-treat population is defined as all subjects who are randomized and receive at least 1 dose of study treatment or sham procedure in Part 1.

The safety population will include all subjects who are randomized and receive at least 1 dose of study treatment or sham procedure in Part 1.

The PK population will include all subjects who are randomized and have at least 1 evaluable postdose or postsham-procedure PK sample.

Part 1**Safety Analysis**

The analysis of safety will be performed on the safety population. The incidence of treatment-emergent AEs and SAEs will be tabulated. Changes from baseline in clinical laboratory parameters, vital signs, and ECG parameters will be summarized. Incidence of clinically relevant changes from baseline in vital signs and ECGs will be summarized. Laboratory parameters will also be summarized using shift tables, as appropriate.

PK Analysis

Summary statistics for plasma and CSF concentrations of Nusinersen will be provided.

Exploratory Analysis

For continuous endpoints, the mean change from baseline will be estimated with 95% confidence limits. For categorical outcomes, the proportion of subjects attaining a specified category will be estimated. Selected endpoints may be pooled across subsets as appropriate.

Part 2

No formal statistical analyses will be performed. Descriptive statistics will be presented for safety and efficacy data collected.

Interim Analysis: No formal interim analyses are planned. However, if the Sponsor decides to terminate Part 1 early, data prior to the unblinding of the first subject in Part 1 may be archived; no analyses are planned to be conducted based on the archived data. Full analysis of Part 1 data will be done following database lock at the end of Part 1.

Sample Size Determination: Since this study is exploratory, sample size determination will not be based on power consideration. The sample size considered for this study will allow exploration of safety, tolerability, and selected efficacy endpoints in the selected study population.

CONFIDENTIAL

The information contained herein may not be used, disclosed, or published without the written consent of Biogen MA Inc.

Study Stopping
Rules:

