16.2.2.4. ECGs

ECG results will be presented by subject, and as appropriate, results will be summarized descriptively for each treatment group. The number and percentage of subjects with shifts from baseline normal to each of the categorical values denoting normal, abnormal clinically significant, and abnormal (not clinically significant) will be summarized.

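### The ECG shift table in SAP 5.3 uses adverse-event labels that match neither the recorded ECG values nor the protocol, and it leaves worsening from an abnormal baseline to a listing

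*SAP*

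**What the plan says.** SAP 5.3 describes the data first: "ECG qualitative results include an overall interpretation of 'normal', 'abnormal but not clinically significant' or 'abnormal and clinically significant". It adds: "Quantitative results will not be captured in the clinical database". It then defines the summary as "The number and percentage of subjects with shifts from normal to each of the categorical values denoting an abnormal scan", and names the two abnormal categories by whether they are adverse events: "abnormal not AE, abnormal AE) will be summarized by treatment group". One further display is planned: "A listing of subjects with abnormal status in ECG will be presented".

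Protocol 16.2.2.4 plans the same kind of table, also starting from a normal baseline, but with end categories that match the recorded values: "normal, abnormal clinically significant, and abnormal (not clinically significant) will be summarized". It also says ECG results will be presented subject by subject.

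Change from baseline in ECGs is part of the primary safety endpoint for both parts (Protocol 6.1; SAP, Description of Objectives and Endpoints, 1.1).

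**The concern.** The two halves of SAP 5.3 do not fit together. Clinical significance is part of the interpretation recorded for the ECG. Adverse-event status is a separate decision, made by the investigator under Protocol 15.1.1 and 15.2.1. Neither document gives a rule for passing from one to the other, so whoever programs the table must invent a mapping, and different mappings could give different counts.

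The starting state is a second weakness. A child whose ECG is abnormal but not clinically significant at baseline, and later becomes clinically significant, has worsened in the way a safety summary is meant to show. That child has no cell in the table. No numerical ECG result is in the database, so no other ECG summary would show the change as a count or percentage by group.

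**Working it through.** The plan gives no figure to reproduce. The check compares the texts and counts cells. Below, N is normal, NCS is abnormal not clinically significant, and CS is abnormal clinically significant.

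**Step 1: categories side by side**

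| Source | Abnormal categories |
|---|---|
| Values recorded (SAP 5.3, data description) | NCS, CS |
| Protocol 16.2.2.4 shift table | CS, NCS |
| SAP 5.3 shift table | not an AE, an AE |

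The protocol's labels match 2 of the 2 recorded abnormal values; the SAP's match 0 of 2. A not-an-AE label does occur in the protocol, but for the neurological examination (16.2.2.1). The SAP wording may have been carried over from there, though that is only an inference.

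**Step 2: transitions covered**

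Three baseline states by three post-baseline states give 3 x 3 = 9 cells. Three of these are worsening: N to NCS, N to CS, and NCS to CS. A table that starts only from N holds the first two, so coverage is 2 of 3. Correcting the labels alone leaves coverage at 2 of 3. Adding all baseline rows makes it 3 of 3.

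**Step 3: can an NCS baseline occur?**

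Yes. Exclusion criterion 7 (Protocol 8.2) removes a child for an ECG abnormality only if it is clinically significant and makes the child unsuitable. Previous-control children take a new baseline before their first Part 2 dose (Protocol 16), and the Part 2 exclusion criterion rests on investigator judgement about a significant change in clinical status.

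**Step 4: how the SAP treats laboratory shifts**

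In SAP 5.2, shift to high admits low, normal and unknown baselines and uses the maximum post-baseline value. Shift to low is the mirror image. SAP 5.3 gives no equivalent rule for a non-normal or missing baseline, and does not say which post-baseline ECG counts. Several are scheduled (Protocol Tables 2 to 4).

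**Step 5: how many children could be outside the table?**

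The documents do not give the proportion q with an abnormal baseline ECG, so q is an assumption here. The planned maximum is n = 21 (Protocol synopsis). The expected number outside the shift count is n x q, and the chance of at least one is 1 - (1 - q)^n.

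| Assumed q | 21 x q | 1 - (1 - q)^21 |
|---|---|---|
| 5% | 1.1 | 66% |
| 10% | 2.1 | 89% |
| 25% | 5.2 | 99.8% |
| 50% | 10.5 | about 100% |

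These are children who start abnormal and so have no row. They are not children who worsen, and nothing in the documents allows that number to be estimated.

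**The case against.** The case against has five parts.

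- **Producibility.** A reader might infer that the primary ECG endpoint cannot be produced. The documents do not support that. The protocol's table can be built from the recorded field, and so can the listing. The SAP also says the qualitative results include the interpretation, which is not an exhaustive list of fields. Since the case report form is not among the documents, an adverse-event field cannot be ruled out, and AEs are recorded on the CRF and could in principle be linked. What stands is that no such field or linking rule is described.
- **Visibility.** A reader might infer that worsening from an abnormal baseline is lost altogether. It is not. A child moving from NCS to CS belongs in the abnormal-ECG listing and in the protocol's by-subject presentation. If the change is reported as an AE, it also enters the AE tables. With at most 21 children and no formal testing, a listing is workable. What stands is that it gives no count or percentage by group.
- **Origin.** Starting only from normal is the protocol's own rule, so on this point the SAP is consistent with it. Adding baseline rows is an improvement rather than the repair of a discrepancy.
- **ECG measurements.** The protocol synopsis says "Changes from baseline in clinical laboratory parameters, vital signs, and ECG parameters will be summarized", which might suggest that ECG intervals are owed here. That sentence sits under Part 1, whose planned analysis SAP Section 1 assigns to a separate SAP. Protocol 16.2.2.4 names no intervals, and no document says the central reader holds a usable interval file. This objection stands in full.
- **Size.** A reader might say that every row is affected, or that each omitted child shifts the result by 1/21 = 4.8 points. The mismatch concerns the two abnormal labels, and no count is shown to change. The 4.8 also uses the planned maximum and applies only to a column holding all 21; in groups of the planned sizes 14 and 7, one child is 7.1% or 14.3%.

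**Conclusion.** The point holds in limited form and is minor. As written, the shift-table labels in SAP 5.3 conflict with the SAP's own description of the data and with Protocol 16.2.2.4, and no ECG-to-AE rule fills the gap. The table also covers 2 of the 3 possible worsening transitions, leaving NCS to CS out of the SAP's only ECG summary for a component of the primary safety endpoint, and visible only in a listing.

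The number of children affected cannot be known from the documents. The range in the working rests entirely on assumed baseline rates and on the planned maximum of 21. The conclusion about the labels needs no assumption beyond reading SAP 5.3 as describing the ECG result that will be tabulated.

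**What to change.** Rewrite the summary paragraph of SAP 5.3 as follows.

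- Use the three recorded categories: normal, abnormal not clinically significant, and abnormal clinically significant.
- Tabulate every baseline category, with a row for missing, against the worst post-baseline ECG. This follows in substance what SAP 5.2 already does for laboratory shifts.
- Present the table by the safety display groups in SAP Section 2, and state the denominator.
- Keep the listing of abnormal ECGs.
- If a split by adverse-event status is also wanted, add it as a separate display and define how an ECG record is linked to an AE record.

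The cost is a change of SAP wording and one table layout. No new data are needed for the three-category table. An AE split would need only the linking rule, or the name of the case report form field if one exists.
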